8.2 Safety and Other Assessments

8.2.1 Demographics and Medical History

Demographic information to be obtained will include date of birth, sex, Hispanic ethnicity, race.

Medical history to be obtained will include determining whether the study participant has any significant conditions or diseases relevant to the disease under study. If available, family history of seizures and delivery complications should be recorded under medical history. Ongoing conditions are considered concurrent medical conditions. Concurrent medical conditions are those significant ongoing conditions or diseases that are present at signing of informed consent. This includes clinically relevant laboratory or physical examination abnormalities noted at Screening. The condition (i.e., diagnosis) must be described.

8.2.2 Pregnancy and Delivery History

Current delivery information will be recorded for the following:

- Date of delivery
- Delivery presentation

- Occiput posterior
- Occiput anterior
- Brow
- Face
- Compound
- Transverse
- Breech
- Other (please specify)
- Unknown

8.2.3 Medical History of Mother

The medical history of the mother will not be recorded.

8.2.4 Apgar Scores

Apgar is a point system routinely used at birth to assess a neonate's vitality at one, five and ten minutes after birth. The scale ranges between 0 and 10, where a score of 10 indicates a baby in full health. Retrospective apgar assessment scores may be used if assessment can't be performed after time of consent.

8.2.5 Physical Examination

A complete physical examination will be done that is limited to the following body systems: general appearance, head and neck, eyes and ears, nose and throat, chest, lungs, heart, abdomen, extremities and joints, lymph nodes, skin, and neurological. A neurologic exam will also be performed as part of safety evaluation.

Neurological exam to include the examination of the following:

- General Exam
 - Newborn reflexes
 - Posture
 - Alertness
 - Level of activity
 - Jitteriness
 - Benign neonatal sleep myoclonus
 - Saccadic Intrusions
 - Periodic breathing
- Cranial Nerve Exam
 - Pupil reflex
 - Doll's Eyes
 - Corneal, sucking and rooting reflexes
 - Response to noise

- Gag reflex

8.2.6 Vital Signs

Temperature, blood pressure, pulse, respiratory rate and O₂ saturation will be recorded. Vital signs will continue to be recorded based on schedule of assessments (Section 1.3).

8.2.7 Clinical Laboratory Determinations

Clinical laboratory tests will be conducted according to the SoA. Clinical laboratory tests to be conducted include complete blood count with differentials, liver panel, basic metabolic panel and coagulation tests (See [Appendix 12.4](#) for list of tests). Clinical laboratory tests will be performed by a designated local or institutional laboratory. PK blood testing will be performed by a Bioanalytical Laboratory. Each site will be provided with instructions on PK specimen collection, preparation, packaging and transport. Refer to the Bioanalytical Laboratory's manual for further information regarding sample collection, handling, and labeling.

Clinical laboratory test data will be reviewed by the PI, or designee, and additional clinical laboratory tests may be ordered at his/her discretion (e.g., if the results of any clinical laboratory test falls outside the reference range or clinical symptoms necessitate additional testing to ensure safety). Any additional testing will be performed by the designated central laboratory.

The PI will review the lab results for clinical significance. Any clinical laboratory test result meeting the PI's or Sponsor's criteria for clinical significance (refer to laboratory manual) will be recorded as an AE or SAE as appropriate.

8.2.7.1 *Blood Sampling for Pharmacokinetic Analysis*

Phenobarbital in neonates (1-10 days old) have been reported to have a half-life of approximately 114±43 hours.

Collection of plasma samples for phenobarbital analysis will be obtained using a population pharmacokinetic approach at the following time points:

- PK Group 1: 30 minutes, 4-6 hours post initial dose,
- PK Group 2: 30 minutes, 10-12 hours post initial dose,
- PK Group 3: 30 minutes, 16-18 hours post initial dose,
- PK Group 4: 30 minutes, 22-24 hours post initial dose,

At the time of randomization to treatment, the IWRS system will also randomize study participants to the 4 PK groups with a 1:1:1:1 allocation. Collection of blood will also occur after the second dose (if applicable). During the Open Label Extension Period, phenobarbital plasma concentrations will be obtained every 24 hours post initial dose up to 120 hours or at time of early discontinuation.

Total blood volume drawn for each PK time point will be approximately 1 mL.

Total blood volume withdrawn per day for clinical labs and PK should be within institution standard of care. If total maximum daily blood volume will be exceeded, the following priority list should be followed:

1. Standard of Care/Institution's Standard of Care Clinical Labs
2. Study related/requested Clinical Labs
3. PK Blood Samples

If study related blood draws are missed, this will be captured as "minor" protocol deviations.

8.2.8 Continuous Video EEG Monitoring

Continuous video-EEG (cvEEG) monitoring is the gold standard for neonatal seizure detection and quantification and should be used whenever available for seizure detection and differential diagnosis of abnormal appearing, paroxysmal clinical events (25). It is the ideal tool to measure the exact number and duration of seizures, their site(s) of onset and spatial patterns of migration. Multichannel (minimum 8-20 channels) cvEEG monitoring is required for accurate detection of seizures to determine drug response (26).

The following are cvEEG reading **recommendations** during the Screening and Treatment Period for the site neurophysiologist or site designee:

- Review first hour of cvEEG recording as soon as possible.
- If not sure if a pattern is a seizure or study participant does not have 30 seconds/hour seizure burden, review every hour for up to 6 hours followed by every 2 hours for up to 4 hours and then every 4 hours.
- If runs of spike/sharp wave discharges or focal discharges, review every 2 hours for up to 6 hours and then review every 4 hours.
- For any other EEG background/pattern- every 4 hour (if normal not to have to wake up midnight to 6 AM).
- Shortly after reports of suspicious clinical event or 1 hour after start of a therapeutic intervention to evaluate for treatment response (assumes 30-minute infusion).

The following are cvEEG reading recommendations during the Follow-up Period and Open Label Maintenance Period:

- Site is to follow their cvEEG reading standard of practice.

It is also **recommended** that the cvEEG technologist or site designee should remain at the monitor for the first hour of recording to ensure a high-quality recording and to make note of relevant clinical signs. Thereafter, the cvEEG technologist or site designee should re-evaluate the quality of the cvEEG recording frequently and adjust recording leads as required by site's standard of practice. It is also **recommended** that the bedside research staff evaluate the quality of the recording periodically and should contact the technologist or designee if the tracing is suboptimal.

cvEEG recording and monitoring will start at time of informed consent or when study participant is hooked up (whichever is latest) and continue up to 48 hours from start time of first phenobarbital dose. cvEEG recording and monitoring after 48 hours is not required per this protocol and will follow site's standard of practice.

Skin assessments as required by institutional standard operating procedures will be allowed. It is recommended that the amount of time the leads are off the study participant are minimized.

At minimum, the entire EEG recording will need to be backed up and archived for the study. Details regarding data transfer for the cvEEG recordings and video clippings are described in the Operational Procedure Manual.

8.2.9 Clinical Seizure Assessment

Clinical manifestations of seizures will be assessed and reported based on the SoA. Research staff will observe the study participants for abnormal behaviors or movements. Research staff should observe for the following (27):

- Ocular, oral-buccal-lingual, autonomic, apnea, limb posturing and movements
- Repetitive jerking, distinct from jittering (can be unifocal or multifocal)
- Rapid isolated jerks (focal, multifocal or generalized)
- Stiffening and/or decerebrate posturing (focal or generalized)

Seizures should also be categorized as either clonic, tonic, myoclonic or subtle.

8.2.10 Assessment of Adverse Events

Adverse Events that are ongoing at the end of the study will be followed until resolution or for 30 days, whichever is shorter.

8.3 Adverse Events and Serious Adverse Events

8.3.1 Definition of Adverse Events (AE)

Adverse event means any untoward medical occurrence associated with the use of a drug in humans, whether or not considered drug-related (21 CFR 312.32 (a)).

An adverse event (also referred to as an adverse experience) can be any unfavorable and unintended sign (e.g., an abnormal laboratory finding), symptom, or disease temporally associated with the use of a drug, and does not imply any judgment about causality. An adverse event can arise with any use of the drug (e.g., off-label use, use in combination with another drug) and with any route of administration, formulation, or dose, including an overdose.

8.3.1.1 Suspected Adverse Reaction

Suspected adverse reaction means any adverse event for which there is a reasonable possibility that the drug caused the adverse event. For the purposes of IND safety reporting, 'reasonable possibility' means there is evidence to suggest a causal relationship between the drug and the adverse event. A suspected adverse reaction implies a lesser degree of certainty about causality than adverse reaction, which means any adverse event caused by a drug (21 CFR 312.32 (a)).

8.3.2 Definition of Serious Adverse Events (SAE)

An adverse event (AE) or suspected adverse reaction is considered "serious" if, in the view of either the investigator or Sponsor, it results in any of the following outcomes: death, a life-threatening adverse event, inpatient hospitalization or prolongation of existing hospitalization, a persistent or significant incapacity or substantial disruption of the ability to conduct normal life functions, or a congenital anomaly/birth defect. Important medical events that may not result in death, be life-threatening, or require hospitalization may be considered serious when, based upon appropriate medical judgment, they may jeopardize the participant and may require medical or surgical intervention to prevent one of the outcomes listed in this definition. Examples of such medical events include allergic bronchospasm requiring intensive treatment in an emergency room or at home, blood dyscrasias or convulsions that do not result in inpatient hospitalization, or the development of drug dependency or drug abuse.

8.3.3 Classification of an Adverse Event

For adverse events (AEs) not included in the protocol defined grading system, the following guidelines will be used to describe severity.

- **Mild:** Events require minimal or no treatment and do not interfere with the participant's daily activities.
- **Moderate:** Events result in a low level of inconvenience or concern with the therapeutic measures. Moderate events may cause some interference with functioning.
- **Severe:** Events interrupt a participant's usual daily activity and may require systemic drug therapy or other treatment. Severe events are usually potentially life-threatening or incapacitating. Of note, the term "severe" does not necessarily equate to "serious".

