3.2.4 Safety Endpoints

The following safety assessments will be performed during the study:

- Type, incidence, and severity of adverse events
- Physical examination (including neurologic exam)
- Vital signs (blood pressure [arterial line], respiration rate, pulse rate, oxygen saturation, and temperature)
- Clinical laboratory tests (hematology, serum chemistry)

3.2.4.1 *Justification for Safety Endpoints*

Safety monitoring is a standard, yet critical component of any clinical trial. The safety assessments in this study are not beyond that of standard safety assessments performed in many clinical studies.

4 Study Design

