5.1 Inclusion Criteria

In order to be eligible to participate in this study, an individual must meet all of the following criteria:

1. Male or female neonates with a gestational age of ≥ 34 - ≤ 44 weeks admitted into the NICU with a high probability of developing seizures (e.g., HIE, stroke, intracerebral hemorrhage, central nervous system infection)
2. Parental/Legal Guardian informed consent (in-person or remote consent)
3. Undergoing continuous video electroencephalogram (cvEEG) monitoring
4. Has evidence of electrographic seizure burden of at least 30 seconds/h

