7.4.2 Stopping rules for Overall Trial

The DSMB may recommend stopping the study for the following reasons:

- The data show a clinically important risk of serious adverse effects in one or both of the treatment arms.
- It becomes clear that successful completion of the study is not feasible (e.g. there is an excess of study participant dropout, missing data, lack of recruitment etc).

7.4.2.1 *Safety-Continuous Monitoring*

Adverse Events will be continuously monitored by the investigator, clinical research associate, CRO Medical Monitor and Sponsor.

If while continuous monitoring the investigator deems an adverse event to be severe, unexpected and possibly related to phenobarbital, the investigator will report the event to NEMA within 24 hours of the event. These unanticipated adverse events will events will also be reported by the PI to the local IRB in accordance with the local IRB policies. NEMA will be responsible for reporting the unanticipated adverse events to all DSMB members within 24 hours of receiving the report, and to the FDA in an IND safety report in accordance with FDA regulations. The DSMB will determine if the adverse event changes the known risk to study participants. If the information changes the known risk to study participants, the DSMB's report regarding the change in risk will be released to all participating investigators by NEMA. The DSMB may request changes to the DSMB Charter and or potentially halt the trial.

7.4.2.2 *Safety-Interim Monitoring*

The DSMB will evaluate the study after the first 10% and 50% of randomized study participants.

Criteria to be evaluated are outlined in detail in the committee charter.

8 Study Assessments and Procedures

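### The only adverse event severity scale has no neonatal anchors, and because 7.4.2.1 triggers on that grade while 8.4.2 triggers on seriousness, some serious events have no prompt DSMB route in the protocol

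*Protocol*

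**What the plan says.** **Endpoint and population.** Protocol 3.2.4 lists "Type, incidence, and severity of adverse events" first among the safety assessments, and SAP 3.7.2 repeats it. Participants are neonates of 34 to 44 gestational "weeks admitted into the NICU with a high probability of developing seizures" (Protocol 5.1).

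**Scale.** Protocol 8.3.3 introduces its three grades this way: "For adverse events (AEs) not included in the protocol defined grading system, the following guidelines will be used to describe severity". The grades are:
- Mild: "Events require minimal or no treatment and do not interfere with the participant's daily activities".
- Moderate: tied to slight inconvenience or concern over treatment, with the addition "Moderate events may cause some interference with functioning".
- Severe: the event interrupts the participant's "usual daily activity and may require systemic drug therapy or other treatment". A further sentence says such events usually threaten life or incapacitate, and another warns that severe and serious are different terms.

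**Use of the grade.** Protocol 7.4.2.1 opens its expedited route with "If while continuous monitoring the investigator deems an adverse event to be severe, unexpected and possibly related to phenobarbital". The investigator then tells NEMA within 24 hours, and NEMA tells all DSMB members within 24 hours of receipt. Section 7.4.1.2 sends events that are expected, unrelated and not severe to the regular DSMB meetings.

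**Use of seriousness.** Under 8.3.6 every serious adverse event goes to the CRO within 24 hours, whatever its relation to the drug. Under 8.4.2 an unanticipated problem that is also a serious adverse event goes to the CRO within 24 hours, and to the IRB and the DSMB or sponsor within 24 hours of CRO awareness. Any other unanticipated problem goes to them within 48 hours. Section 8.4.1 requires all three of its criteria to be met: unexpected, at least possibly related, and suggesting greater risk than was known.

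**The concern.** A sedated, cooled or ventilated newborn has no daily activities to interrupt and cannot report inconvenience. If the activity wording has no meaning in this population, each site must invent its own, and a listed safety endpoint is then recorded on a scale that shifts from site to site.

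The same grade also does operational work. It helps decide which events the DSMB hears about promptly in a trial comparing two loading doses of a drug whose listed reactions include respiratory depression, apnea and hypotension (2.3.1.4). If the alert depends on a grade that cannot be assigned reliably, and 8.3.3 itself separates that grade from seriousness, a serious event could miss the prompt route because of how it was graded.

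**Working it through.** No figure in the plan depends on this point, so the check is textual, with simple arithmetic on the reporting clocks.

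**1. Is there another severity scale?** None appears in the protocol or SAP text supplied. Appendix III lists medical concepts to consider for *seriousness* and attaches a toxicity grade to a few metabolic terms, but it defines no scale. The 8.3.3 fallback therefore applies in effect to every event.

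**2. Can the boundaries be applied?** Take treated hypotension that resolves in a neonate on intensive care.
- Mild allows minimal treatment, but minimal is not defined, and the activity condition cannot be assessed.
- Moderate states no level of treatment. Its tests are inconvenience, concern and functioning.
- Severe mentions drug therapy or other treatment, but only as something that may be needed, joined to an activity condition that cannot be assessed. The threat-to-life sentence can be applied to a neonate, but it says what is usual and sets no criterion.

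Two careful investigators could defend Moderate and Severe for the same event. The top of the scale is recognisable; the Mild/Moderate and Moderate/Severe boundaries are not. Up to 30 sites are planned (5.5.3).

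**3. Which routes reach the DSMB?** Take an event that is serious, unexpected, possibly related, graded Moderate, and not judged to suggest greater risk than was known.

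| Route | Conditions | DSMB timing stated | This event |
|---|---|---|---|
| 7.4.2.1 | Severe, unexpected, possibly related | 24 + 24 = 48 h at most | Not met: grade |
| 8.4.2, serious | Serious and all three 8.4.1 criteria | 24 + 24 = 48 h at most, if the first clock starts at site awareness (start not stated) | Not met: risk criterion |
| 8.4.2, other | All three 8.4.1 criteria, not serious | 48 h from investigator awareness | Not met: it is serious, and it fails the risk criterion |
| 8.3.6 | Serious | None named; CRO within 24 h | Met |
| 7.4.1.2 | Expected, unrelated, not severe | Regular meetings | Not met: unexpected and possibly related |

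**4. Can such an event occur?** Section 8.3.8 makes some events serious by rule, with no reference to grade. Polycythemia and systemic hypertension needing treatment are two. Either could be graded Moderate. Whether one also counts as unexpected is a judgement under 8.3.3.2, and that judgement itself depends partly on intensity.

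**5. How long could the DSMB wait?** Section 10.1.7 sets meetings at least semiannually unless the charter differs: 12 / 2 = 6 months between meetings if evenly spaced. Section 7.4.2.2 adds reviews after 10% and 50% of randomised participants. With the planned 196 these fall at 0.10 × 196 = 19.6, about 20, and 0.50 × 196 = 98.

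**The case against.** The strongest reply is that the protocol already covers most of this.

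First, 7.4.2.1 is not the only 24-hour path to the DSMB. A reader who stops there might infer that it is, but 8.4.2 provides another that turns on seriousness. The event in the working already satisfies two of the three 8.4.1 criteria, and many related, unexpected serious events would satisfy the third. Every serious event also reaches the CRO within 24 hours, and NEMA appears to act in that role, since it supplies the monitors and archives the data, although no section says so outright. This stands, and it makes the gap narrow.

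Second, the Severe definition is not only about activity or treatment. A reader might take the treatment clause alone and infer that most events in supported neonates would be graded Severe. The text does not support that: the clause is permissive, it is joined to another condition, it is followed by the threat-to-life sentence, and no figure is given for how many events need treatment.

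Third, a reader might infer that the primary objective compares severity between doses. The objective speaks only of dose-response for safety and efficacy. The planned analyses (Protocol 9.4.4, SAP 8.1) count treatment-emergent events, discontinuations and serious events by system organ class and preferred term, with no table by grade.

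Fourth, the DSMB charter and the procedures manual are not supplied and may hold a neonatal scale or a further alert rule.

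What these replies leave untouched is the undefined boundaries in 8.3.3, the reference to an unidentified grading system, and two sections with different triggers for the same purpose.

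**Conclusion.** The point holds in a limited form. The scale in 8.3.3 works poorly in this population: its two inner boundaries cannot be applied consistently, although severity is a listed endpoint in both documents. Sections 7.4.2.1 and 8.4.2 use different triggers for prompt DSMB notice, and a serious, unexpected, possibly related event graded Moderate and not judged to raise known risk falls between them.

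How often that would happen cannot be computed, because the documents give no event rates by grade. The delay runs from at most about 48 hours on a prompt route to as long as about 6 months at the minimum meeting frequency. This assumes evenly spaced meetings, no intervening 10% or 50% review, no charter rule and no informal escalation by the CRO or sponsor. The efficacy analysis is unaffected, and so is any planned statistical comparison of safety, because none uses the grade. It is worth correcting because the remedy is cheap and bears on safety monitoring.

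**What to change.** **Section 8.3.3.** Replace the activity-based anchors with neonatal ones that refer to change in care already charted:
- Mild: no change in care.
- Moderate: new or increased treatment or monitoring, not life-threatening.
- Severe: major escalation of respiratory or circulatory support, or life-threatening.

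The CRF guidance should say what counts as major escalation. Identify the grading system that the section refers to, or delete the reference.

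**Sections 7.4.2.1 and 7.4.1.2.** In 7.4.2.1 change *severe* to *severe or serious*. Substituting *serious* alone would remove severe but non-serious events from the current alert. In 7.4.1.2 change *not severe* to *neither severe nor serious*. Reconcile both with 8.3.6 and 8.4.2 so that each class of event has one stated path and clock to the DSMB. That includes serious events that are expected or unrelated, which should not drop out of routine review. Align the charter if it already covers this.

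**Cost.** Protocol wording, CRF guidance and brief site training, plus a few more prompt DSMB notices. No current alert is lost.
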